## 1. Protocol Synopsis

### Title of Study:

A Multiple Dose Titration Study in Chinese Patients with Type 2 Diabetes Mellitus to Investigate the Safety, Tolerability, Pharmacokinetics, Pharmacodynamics, and Efficacy of Tirzepatide.

### Rationale:

Tirzepatide is a dual agonist of glucose-dependent insulinotropic polypeptide and glucagon-like peptide-1 receptors being developed as a weekly treatment for type 2 diabetes mellitus (T2DM). This study of tirzepatide, I8F-MC-GPHT (GPHT), will investigate the safety, tolerability, pharmacokinetics (PK), pharmacodynamics (PD), and efficacy of tirzepatide administered once weekly for 16 or 24 weeks as subcutaneous (SC) injections to Chinese patients with T2DM.

### Objective(s)/Endpoints:

Objectives	Endpoints
Primary	
To investigate the safety and tolerability of tirzepatide after multiple SC doses administered to Chinese patients with T2DM	Incidence of TEAEs
Secondary	
To characterize the PK of tirzepatide after multiple SC doses in Chinese patients with T2DM	AUC and $C_{max}$ of tirzepatide

Abbreviations: AUC = area under the concentration-time curve;  $C_{max}$  = maximum observed drug concentration; PK = pharmacokinetics; SC = subcutaneous; 7p-SMPG = 7-point self-monitored plasma glucose; T2DM = type 2 diabetes mellitus.

### Summary of Study Design:

Study GPHT is a Phase 1, randomized, placebo-controlled, multiple dose titration study in Chinese patients with T2DM.

### Treatment Arms and Planned Duration for an Individual patient:

This study consists of 2 cohorts. Approximately 12 Chinese patients with T2DM will be randomized within a cohort to receive tirzepatide or placebo. For Cohort 1, 16 weekly SC doses of tirzepatide or placebo will be administered in a ratio of 10 tirzepatide:2 placebo. For Cohort 2, 24 weekly SC doses of tirzepatide or placebo will be administered in a ratio of 10 tirzepatide:2 placebo.

Patients in Cohort 1 will receive either tirzepatide with titration regimen starting from 2.5 mg for Days 1, 8, 15, and 22 (Weeks 0 to 3), 5 mg for Days 29, 36, 43, and 50 (Weeks 4 to 7), 7.5 mg for Days 57, 64, 71, and 78 (Weeks 8 to 11), and 10 mg for Days 85, 92, 99, and 106 (Weeks 12 to 15), or corresponding volume-matched placebo.

Patients in Cohort 2 will receive either tirzepatide with titration regimen starting from 2.5 mg for Days 1, 8, 15, and 22 (Weeks 0 to 3), 5 mg for Days 29, 36, 43, and 50 (Weeks 4 to 7), 7.5 mg for Days 57, 64, 71, and 78 (Weeks 8 to

11), 10 mg for Days 85, 92, 99, and 106 (Weeks 12 to 15), 12.5 mg for Days 113, 120, 127, and 134 (Weeks 16 to 19), and 15 mg for Days 141, 148, 155, and 162 (Weeks 20 to 23), or corresponding volume-matched placebo.

**Number of Patients:**

Approximately 24 Chinese patients with T2DM may be enrolled to ensure approximately 16 patients complete the study, in compliance with the defined dosing regimen.

**Statistical Analysis:**

Pharmacokinetics, PD, and efficacy analyses will be conducted on data from all patients who receive at least 1 dose of the IP and have evaluable PK, PD, and efficacy data. Safety analyses will be conducted for all enrolled patients, whether or not they completed all protocol requirements.

**Safety:** All IP and protocol procedure-related adverse events will be listed, and if the frequency of events allows, safety data will be summarized using descriptive methodology. Safety parameters that will be assessed include safety laboratory parameters, vital signs, electrocardiogram parameters, injection-site reactions, and hypoglycemia.

**Efficacy:** The efficacy of tirzepatide to reduce glucose and weight will be assessed. All parameters will be listed and summarized using standard descriptive statistics.

**Pharmacodynamics:** Lipids and subjective appetite sensation (VAS) will be listed and summarized using descriptive methodology.

**Pharmacokinetics:** The primary parameters for analysis will be maximum drug concentration ( $C_{max}$ ), area under the concentration-time curve (AUC), and time to  $C_{max}$  ( $T_{max}$ ) of tirzepatide. Other noncompartmental parameters, such as half-life, apparent clearance, and apparent volume of distribution may be reported. Pharmacokinetic parameters will be summarized using descriptive statistics. The mean concentration-time profiles in linear and semilog scale for each tirzepatide-treated group will be presented.

**Immunogenicity:** The frequency and percentage of subjects/patients with preexisting antidrug antibodies (ADAs) and with treatment-emergent (TE) ADA to tirzepatide will be tabulated. The frequency of neutralizing antibodies to tirzepatide and/or cross-reactive to endogenous counterparts may also be tabulated in TE ADA patients.

The relationship between the presence of antibodies, antibody titres, and clinical parameters (for example, AEs) may be assessed. Likewise, the relationship between antibody titers, PK parameters, and PD response to tirzepatide may be assessed.

## 2. Schedule of Activities

## Study Schedule Protocol I8F-MC-GPHT Cohort 1 Except for Treatment Period

Procedure	Screening	Lead-in	Treatment Period	Follow-Up		
Days	Day -28 ~ -17	Day -14 ±1		Day 120 ±2	Day 141 ±2	ED2 a
Outpatient Visit	1	2		13	14	
Fasting Visitb	X				X	X
Informed Consent	X					
Outpatient Visit	X	X		X	X	X
Dispense Study Diary & Training		X				
BG Meters/Test Stripes Dispense & Training		X				
Study Drug Injection Training		X				
Medical History	X					
Pre-existing Disease and AEs	X	X		X	X	X
Hypoglycemic Events	X	X		X	X	X
Concomitant Treatment	X	X		X	X	X
Height, Race	X					
Body Weight c	X				X	X
Body Temperature	X				X	X

Procedure	Screening	Lead-in	Treatment Period	Follow-Up		
Days	Day -28 ~ -17	Day -14 ±1		Day 120 ±2	Day 141 ±2	ED2 a
Outpatient Visit	1	2		13	14	
Fasting Visit b	X				X	X
Vital Signs (BP/PR)	X				X	X
Physical Examinations d	X				X	X
12-lead ECG	X				X	X
Chest X-Ray e	X					
Clinical Safety Lab (Hematology, Chemistry, Urinalysis) f	X				X	X
Clinical Safety Lab (Pancreatic Enzyme) f	X				X	X
Serology (HBV/HCV/HIV) f	X					
Urine Drug and Alcohol Screen f,g	X					
Pregnancy Test, FSH f,h	X					
Calcitonin	X					
Hemoglobin A1c	X					
7-Point SMPG		X i				

Procedure	Screening	Lead-in	Treatment Period	Follow-Up		
Days	Day -28 ~ -17	Day -14 ±1		Day 120 ±2	Day 141 ±2	ED2 a
Outpatient Visit	1	2		13	14	
Fasting Visit b	X				X	X
PK Sampling j				X	X	X
Immunogenicity					X	X

## Study Schedule Protocol I8F-MC-GPHT Cohort 1 for Treatment Period

Treatment Period	2.5 mg						5 mg					7.5 mg		10 mg												
Week	0			1	2	4	6		7			8	10	12	13	14	15				16					
Day	-1	1	2	3	4	8	15 ±1	29 ±1	43 ±1	9	50	51	52	53	57 ±1	71 ±1	85 ±1	92 ±1	99 ±1	10 5	10 6	10 7	10 8	10 9	11 3	ED 1 a
Visit	V 3	V3 a	V 3b	V 3c	V 3d	V4	TV	V5	TV	V 6	V6 a	V 6b	V 6c	V 6d	V7	TV	V8	V9 0	V1 11	V1 1a	V1 1b	V1 1c	V1 1d	V1 2		
Fasting Visit b		X				X		X		X					X		X		X				X	X		
Admission to CRU	X									X									X							
Inpatient stay at CRU k	X	X	X	X	X					X	X	X	X	X					X	X	X	X	X			
Discharge from CRU					X									X									X			
Outpatient Visit						X		X							X		X	X	X					X		
Randomization		X																								
Dose Administration l		X				X	X	X	X	X					X	X	X	X	X		X					
Pre-existing Disease and AEs	X	X	X	X	X	X	X	X	X	X	X	X	X	X	X	X	X	X	X	X	X	X	X			
Hypoglycemic Events	X	X	X	X	X	X	X	X	X	X	X	X	X	X	X	X	X	X	X	X	X	X	X			
Concomitant Treatment	X	X	X	X	X	X	X	X	X	X	X	X	X	X	X	X	X	X	X	X	X	X	X			
Body Temperature	X	Pre																						X		

Treatment Period	2.5 mg						5 mg					7.5 mg		10 mg												
Week	0			1	2	4	6		7			8	10	12	13	14	15			16						
Day	-1	1	2	3	4	8	15 ±1	29 ±1	43 ±1	4 9	50	51	52	53	57 ±1	71	85 ±1	92 ±1	99	10 5	10 6	10 7	10 8	10 9	11 3	ED 1 a
Visit	V 3	V3 a	V 3b	V 3c	V 3d	V4	TV	V5	TV	V 6	V6 a	V 6b	V 6c	V 6d	V7	TV	V8	V9	V1 0	V 11	V1 1a	V1 1b	V1 1c	V1 1d	V1 2	
Fasting Visit b		X				X		X		X				X		X		X				X	X			
Vital Signs (BP/PR)	X	Pre 2h, 4h, 8h	24 h	48 h	72 h	Pre		Pre		Pre				Pre		Pre		Pre					X	X		
Physical Examinations d																								X		
12-lead ECG	X	Pre	24 h	48 h	72 h	Pre		Pre		Pre				Pre		Pre		Pre	24h	48 h	72h	X	X			
Clinical Safety Lab (Hematology, Chemistry, Urinalysis) f	X		24 h	48 h	72 h	Pre		Pre						Pre		Pre		Pre					X	X		
Clinical Safety Lab (Pancreatic Enzyme) f	X	Pre						Pre						Pre		Pre		Pre					X	X		
Calcitonin		Pre																						X	X	
Hemoglobin A1c		Pre						Pre						Pre		Pre							X	X		
7-Point SMPG	X					X		X						X			X						X			
FBG		Pre				Pre		Pre						Pre		Pre							X			
Lipid Panel		Pre				Pre		Pre						Pre		Pre							X			

Treatment Period	2.5 mg						5 mg					7.5 mg		10 mg												
Week	0			1	2	4	6		7			8	10	12	13	14	15			16						
Day	-1	1	2	3	4	8	15 ±1	29 ±1	43 ±1	4 9	50	51	52	53	57 ±1	71	85 ±1	92 ±1	99	10 5	10 6	10 7	10 8	10 9	11 3	ED 1 a
Visit	V 3	V3 a	V 3b	V 3c	V 3d	V4	TV	V5	TV	V 6	V6 a	V 6b	V 6c	V 6d	V7	TV	V8	V9	V1 0	V 11	V1 1a	V1 1b	V1 1c	V1 1d	V1 2	
Fasting Visit b		X				X		X		X				X		X						X	X			
Body Weight c		Pre				Pre		Pre						Pre		Pre		Pre					X			
Meal Intake and Appetite m	L/ D		L/ D								L/ D								L/ D							
PK Sampling j		Pre D, 8h	24 h	48 h	72 h	16 8h		Pre D			Pre D, 8h	24 h	48 h	72 h	Pre D		Pre D	Pre D	Pre D, 8h	24h	48 h	72h	16 8h	X		
Immunogenicity		Pre						Pre						Pre		Pre							X	X		
Pharmacogenetic Samples		Pre																								

## Study Schedule Protocol I8F-MC-GPHT Cohort 2 except for Treatment Period

Procedure	Screening	Lead-in	Treatment Period	Follow-Up		
Days	Day -28 ~ -17	Day -14 ±1		Day 176 ±2	Day 197 ±2	ED2 a
Outpatient Visit	1	2		15	16	
Fasting Visit b	X				X	X
Informed Consent	X					
Lead-in		X				
Outpatient Visit	X	X		X	X	X
Dispense Study Diary & Training		X				
BG Meters/Test Stripes Dispense & Training		X				
Study Drug Injection Training		X				
Medical History	X					
Pre-existing Disease and AEs	X	X		X	X	X
Hypoglycemic Events	X	X		X	X	X
Concomitant Treatment	X	X		X	X	X
Height, Race	X					

Procedure	Screening	Lead-in	Treatment Period	Follow-Up		
Days	Day -28 ~ -17	Day -14 ±1		Day 176 ±2	Day 197 ±2	ED2 a
Outpatient Visit	1	2		15	16	
Fasting Visit b	X				X	X
Body Weight c	X				X	X
Body Temperature	X				X	X
Vital Signs (BP/PR)	X				X	X
Physical Examinations d	X				X	X
12-lead ECG	X				X	X
Chest X-Ray e	X					
Clinical Safety Lab (Hematology, Chemistry, Urinalysis) f	X				X	X
Clinical Safety Lab (Pancreatic Enzyme) f	X				X	X
Serology (HBV/HCV/HIV) f	X					
Urine Drug and Alcohol Screen f,g	X					
Pregnant Test, FSH f,h	X					
Calcitonin	X					

Procedure	Screening	Lead-in	Treatment Period	Follow-Up		
Days	Day -28 ~ -17	Day -14 ±1		Day 176 ±2	Day 197 ±2	ED2 a
Outpatient Visit	1	2		15	16	
Fasting Visit b	X				X	X
Hemoglobin A1c	X					
7-Point SMPG		X i				
PK Sampling j				X	X	X
Immunogenicity					X	X

## Study Schedule Protocol I8F-MC-GPHT Cohort 2 for Treatment Period

Treatment Period	2.5 mg					5 mg					7.5 mg			10 mg		12.5 mg		15 mg												
Week	0			1	2	4	6		7			8	10	12	14	16	18	20	21	22		23			24					
Day	1	1	2	3	4	8	15 ± 1	29 ± 1	43 ± 1	49	50	51	52	53	57	71 ± 1	85 ± 1	99 ± 1	11 3± 1	12 7± 1	14 1± 1	14 8± 1	15 5± 1	16 1± 1	16 2	16 3	16 4	16 5	16 9	ED 1 a
Visit	V 3	V 3a	V 3b	V 3c	V 3d	V 4	T V	V 5	T V	V 6	V 6a	V 6b	V 6c	V 6d	V 7	T V	V 8	T V	V9	T V	V1 0	V1 1	V1 2	V1 3	V 13a	V 13b	V 13c	V 13d	V 14	
Fasting Visit b		X				X		X							X		X							X						
Admission to CRU	X								X															X						
Inpatient stay at CRU k	X	X	X	X	X				X	X	X	X	X										X	X	X	X	X			
Discharge from CRU					X								X														X			
Outpatient Visit						X		X							X		X		X		X	X	X					X	X	
Randomization		X																												
Dose Administration l		X				X	X	X	X		X				X	X	X	X	X	X	X	X	X	X		X				
Pre-existing Disease and AEs	X	X	X	X	X	X	X	X	X	X	X	X	X	X	X	X	X	X	X	X	X	X	X	X	X	X	X	X	X	

Treatment Period	2.5 mg					5 mg					7.5 mg		10 mg		12.5 mg		15 mg														
Week	0				1	2	4	6		7			8	10	12	14	16	18	20	21	22		23			24					
Day	-1	1	2	3	4	8	15 $\pm$ 1	29 $\pm$ 1	43 $\pm$ 1	49	50	51	52	53	57	71 $\pm$ 1	85 $\pm$ 1	99 $\pm$ 1	11 $\pm$ 1	12 $\pm$ 1	14 $\pm$ 1	14 $\pm$ 1	15 $\pm$ 1	16 $\pm$ 1	162	163	164	165	169	ED1 a	
Visit	V3	V3a	V3b	V3c	V3d	V4	TV	V5	TV	V6	V6a	V6b	V6c	V6d	V7	TV	V8	TV	V9	TV	V10	V11	V12	V13	V13a	V13b	V13c	V13d	V14		
Fasting Visit b		X				X		X		X					X		X		X				X								
Hypoglycemic Events	X	X	X	X	X	X	X	X	X	X	X	X	X	X	X	X	X	X	X	X	X	X	X	X	X	X	X				
Concomitant Treatment	X	X	X	X	X	X	X	X	X	X	X	X	X	X	X	X	X	X	X	X	X	X	X	X	X	X	X				
Body Temperature	X	Pre																										X			
Vital Signs (BP/PR)	X	Pre, 2h, 4h, 8h	24h	48h	72h	Pre		Pre		Pre		Pre		Pre		Pre		Pre		Pre		Pre		Pre		Pre		X	X		
Physical Examinations d																												X			
12-lead ECG	X	Pre	24h	48h	72h	Pre		Pre		Pre		Pre		Pre		Pre		Pre		Pre		Pre		Pre		Pre	24h	48h	72h	X	X

Treatment Period	2.5 mg					5 mg					7.5 mg		10 mg		12.5 mg		15 mg													
Week	0				1	2	4	6		7			8	10	12	14	16	18	20	21	22		23			24				
Day	1	1	2	3	4	8	15 $\pm$ 1	29 $\pm$ 1	43 $\pm$ 1	49	50	51	52	53	57	71 $\pm$ 1	85 $\pm$ 1	99 $\pm$ 1	113 $\pm$ 1	127 $\pm$ 1	141 $\pm$ 1	148 $\pm$ 1	155 $\pm$ 1	161 $\pm$ 1	162	163	164	165	169	ED1 a
Visit	V3	V3a	V3b	V3c	V3d	V4	TV	V5	TV	V6	V6a	V6b	V6c	V6d	V7	TV	V8	TV	V9	TV	V10	V11	V12	V13	V13a	V13b	V13c	V13d	V14	
Fasting Visit b		X				X		X		X					X		X		X				X							
Clinical Safety Lab (Hematology, Chemistry, Urinalysis) f	X		24h	48h	72h	Pre		Pre							Pre		Pre		Pre									X	X	
Clinical Safety Lab (Pancreatic Enzyme) f	X	Pre						Pre							Pre		Pre		Pre									X	X	
Calcitonin		Pre																											X	X
Hemoglobin A1c		Pre						Pre							Pre		Pre		Pre									X	X	
7-Point SMPG	X					X		X							X		X		X				X					X		

Treatment Period	2.5 mg					5 mg					7.5 mg		10 mg		12.5 mg		15 mg													
Week	0				1	2	4	6		7			8	10	12	14	16	18	20	21	22		23			24				
Day	-1	1	2	3	4	8	15 $\pm$ 1	29 $\pm$ 1	43 $\pm$ 1	49	50	51	52	53	57	71 $\pm$ 1	85 $\pm$ 1	99 $\pm$ 1	11 $\pm$ 1	12 $\pm$ 1	14 $\pm$ 1	14 $\pm$ 1	15 $\pm$ 1	16 $\pm$ 1	162	163	164	165	169	ED1 a
Visit	V3	V3a	V3b	V3c	V3d	V4	TV	V5	TV	V6	V6a	V6b	V6c	V6d	V7	TV	V8	TV	V9	TV	V10	V11	V12	V13	V13a	V13b	V13c	V13d	V14	
Fasting Visit b		X				X		X							X		X							X						
FBG		Pre				Pre		Pre							Pre		Pre		Pre		Pre								X	
Lipid Panel		Pre				Pre		Pre							Pre		Pre		Pre		Pre								X	
Body Weight c		Pre				Pre		Pre							Pre		Pre		Pre		Pre								X	
Meal Intake and Appetite m	L/D	L/D									L/D														L/D					
PK Sampling j		PreD, 8h	24h	48h	72h	168h		PreD			PreD, 8h	24h	48h	72h	168h		PreD		PreD		PreD		PreD		PreD, 8h	24h	48h	72h	168h	X
Immuno genicity		Pre						Pre							Pre		Pre												X	X
Pharmacogenetic Samples		Pre																												

Abbreviations: AE= adverse event; BG=blood glucose; BP=blood pressure; CRU = clinical research unit; ECG=electrocardiogram; ED=early discontinuation; FBG=fasting blood glucose; FSH = follicle-stimulating hormone; HBV = hepatitis B virus; HCV = hepatitis C virus; HIV = human immunodeficiency virus; IP=investigational product; lab = laboratory; L/D = lunch and dinner; PK = pharmacokinetics; PR=pulse rate; Pre = predose; PreD = predose for PK sampling; SC = subcutaneous; SMPG=self-monitored plasma glucose; TV=telephone visit; V = visit.

a A patient who discontinues from Cohort 1 between Day 1 and Day 113, inclusive, will complete ED1 procedures as soon as possible. The patient will be asked to complete ED2 procedures after a washout period of at least 28 days from the last IP administration. The patient who discontinues from Cohort 1 after the completion of Day 113 will complete ED2 procedures after a washout period of at least 28 days from the last IP administration. A patient who discontinues from Cohort 2 between Day 1 and Day 169, inclusive, will complete ED1 procedures as soon as possible. The patient will be asked to complete ED2 procedures after a washout period of at least 28 days from the last IP administration. The patient who discontinues from Cohort 2 after the completion of Day 169 will complete ED2 procedures after a washout period of at least 28 days from the last IP administration.

b Patients will be required to fast overnight for at least 8 hours before taking the first SC dose of tirzepatide (or placebo) and before each blood sample draw on fasting visit.

c Weight will be measured in a consistent way per Section 9.1, always predose.

d Full physical examination / medical assessment at screening. Symptom-directed physical examination/medical assessment at all other time points, and as deemed necessary by the investigator.

e Patients who have completed chest x-ray within the past 12 months and whose x-ray and/or report are available for review are exempt from the chest x-ray examination. The required chest x-ray is a single posterior anterior (PA) x-ray. If evidence of an abnormality, a lateral chest x-ray will be performed.

f These tests will be performed at the local laboratory.

g Additional urine drug screen or breath ethanol tests may be performed at the investigator's discretion.

h Females only. Blood pregnancy test will be done on screening; urine test at other times as indicated, or when performed at the investigator's discretion.

i Patients will conduct the 7-point SMPG every 3 days since Day -13 during lead-in period and will record readings in patient diary.

j A maximum of 3 samples may be collected at additional time points during the study if warranted and agreed upon by both the investigator and sponsor.

k Patients may be required to remain at the CRU longer than the planned discharge day at the investigator's discretion to assure patients' safety or to provide additional safety monitoring.

l If a dose of tirzepatide is missed, the patient should take it as soon as possible unless it is within 72 hours of the next dose in which case, that dose should be skipped and the next dose should be taken at the appropriate time. In Cohort 1, apart from time points indicated in SOA, tirzepatide should also be administered in Weeks 3, 5, 9, and 11. In Cohort 2, apart from time points indicated in SOA, tirzepatide should also be administered in Weeks 3, 5, 9, 11, 13, 15, 17, and 19.

m Meal intake and subjective rating of appetite sensation will be evaluated before and 4 to 5 hours after standardized lunch and dinner meals on Days -1 and 2 Day 51 (for both cohorts), and Day 107 for Cohort 1 and Day 163 for Cohort 2. The standardized lunch and dinner meals will be provided at least 4 hours after the previous meal. The subjective rating of appetite sensations is measured using a 100-mm visual analogue scale (VAS) for parameters of hunger, fullness, satiety, and prospective food consumption before and 4 to 5 hours after the standardized lunch and dinner meals. Refer to Section 9.6.2 for details.

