## 6. Study Population

Eligibility of patients for the study will be based on the results of screening medical history, physical examination, vital signs, clinical laboratory tests, and ECG.

A chest x-ray will be completed at screening unless one has been obtained within the past 12 months, and the x-ray and/or report are available for review. For this study, the required chest x-ray is a single posterior anterior (PA) x-ray. Only if the PA x-ray shows evidence of an abnormality, a lateral chest x-ray will be performed.

The nature of any conditions present at the time of the physical examination and any preexisting conditions will be documented.

Screening may occur up to Day -28 to Day -17 prior to enrollment. Patients who are not enrolled within 12 days of screening may be subjected to an additional medical assessment and/or clinical measurements to confirm their eligibility.

Prospective approval of protocol deviations to recruitment and enrollment criteria, also known as protocol waivers or exemptions, is not permitted.

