### 6.1. Inclusion Criteria

Patients are eligible for inclusion in the study only if they meet all of the following criteria at screening:

[1] Chinese males or females with T2DM between the ages of 20 and 70 years, inclusive, at screening. Native Chinese is defined as a patient who has all 4 biological grandparents and both biological parents to be of Chinese origin

[1a] male patients:

agree to use an effective method of contraception (barrier contraceptives such as latex condoms) for the duration of the study and or at least 3 months after the last dose of IP

[1b] female patients:

women not of childbearing potential because of surgical sterilization (hysterectomy or bilateral oophorectomy or tubal ligation) or menopause; women with an intact uterus are deemed postmenopausal if they are aged 45 years or older, and

- who have not taken hormones or oral contraceptives within the past year and have had cessation of menses for at least 1 year

OR

- who had at least 6 months of amenorrhoea with follicle-stimulating hormone (FSH) and estradiol levels consistent with a postmenopausal state (FSH  $\geq 40$  mIU/mL and estradiol  $< 30$  pg/mL)

OR

women patients of childbearing potential (not surgically sterilized and between menarche and 1-year postmenopausal) must

- test negative for pregnancy at Visit 1 based on a serum pregnancy test

AND

- if sexually active, agree to use 2 forms of effective contraception, where at least 1 form is highly effective for the duration of the trial and for 30 days thereafter

- [2] have T2DM controlled with diet and exercise alone or are stable on a single OAM, metformin, acarbose, or sulphonylureas only (other types of OAM [DPP-IV inhibitors, sodium-glucose cotransporter-2 inhibitors, and thiazolidinediones] are not allowed in this study), for at least 3 months
- [3] have a HbA1c  $\geq 7.0\%$  and  $\leq 10.5\%$  for patients treated with diet and exercise only, and for the patients treated with antidiabetic medications, HbA1c  $\geq 6.5\%$  and  $\leq 10.0\%$ , at screening visit
- [4] have a body mass of  $\geq 23$  kg/m^2, inclusive
- [5] have clinical laboratory test results within normal reference range for the population or study site, or results with acceptable deviations that are judged to be not clinically significant by the investigator; abnormalities of blood glucose, serum lipids, urinary glucose, and urinary protein consistent with T2DM are acceptable

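### The last required pregnancy test is 17 to 28 days old at the first dose; a urine test on Day -1 would make it 1 day old

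*Protocol*

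**What the plan says.** Inclusion criterion [1b] (protocol section 6.1) admits a woman of childbearing potential if she "test negative for pregnancy at Visit 1 based on a serum pregnancy test". If sexually active, she must also "agree to use 2 forms of effective contraception, where at least 1 form is highly effective". The lead-in to section 6.1 applies the criteria at one time: "Patients are eligible for inclusion in the study only if they meet all of the following criteria at screening".

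The Schedule of Activities marks the test at Visit 1 only. The row is "Pregnancy Test, FSH" in Cohort 1 and "Pregnant Test, FSH" in Cohort 2, and neither treatment-period table has such a row. Footnote h says "Blood pregnancy test will be done on screening; urine test at other times as indicated", or when the investigator chooses. Appendix 2 attaches to the pregnancy test a footnote (c) that makes it a matter of clinical indication and investigator discretion. Appendix 5 allows for one screening sample covering serology and the serum pregnancy test.

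Section 6 adds an optional re-check: "Patients who are not enrolled within 12 days of screening may be subjected to an additional medical assessment", clinical measurements, or both. It names no particular test.

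Patients are admitted on Day -1 (section 5.1). On that day both treatment-period schedules mark the row that begins "Clinical Safety Lab (Hematology, Chemistry, Urinalysis", so urine is already being collected.

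**The concern.** The protocol makes a negative pregnancy test a condition of entry, yet at first exposure that condition can rest on a result two and a half to four weeks old. A pregnancy that became detectable after Visit 1 could go unnoticed when the first dose is given. This includes one conceived shortly before Visit 1 and too early to detect then, which an agreement at screening to use contraception cannot prevent.

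A first dose cannot be withdrawn quickly. Section 3.2 gives a half-life of about 5 days, so five half-lives take about 5 × 5 = 25 days. Section 9.2.1 arranges for a pregnancy to be reported and its outcome collected, which happens after exposure and does not prevent it.

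The size of the harm cannot be stated. The documents give no reproductive-toxicity data, and section 3.3 refers to the Investigator's Brochure for risks.

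**Working it through.** The plan states no figure for the age of the pregnancy result, so there is none to reproduce. The check is day arithmetic on the schedule.

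**Inputs**
- Visit 1 window: Day -28 to Day -17 (Schedule of Activities; section 6).
- Admission: Day -1 (section 5.1). First dose: Day 1 (synopsis; Visit 3a in the schedule).
- The schedule goes from Day -1 to Day 1 with no Day 0.
- Re-check trigger: 12 days from screening to enrolment (section 6). Appendix 1 defines enrolment as treatment assignment, which section 7.2 places at Visit 3a, that is, Day 1.
- Size: 2 cohorts of about 12, each 10 tirzepatide to 2 placebo (synopsis).

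**Age of the last required result at the first dose**

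With no Day 0, elapsed days from a negative day d to Day 1 = (1 − d) − 1.

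| Test day | Calculation | Age at Day 1 |
|---|---|---|
| Day -28 | (1 + 28) − 1 | 28 days |
| Day -17 | (1 + 17) − 1 | 17 days |
| Day -1 (proposed) | (1 + 1) − 1 | 1 day |

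Reduction: 17 − 1 = 16 days to 28 − 1 = 27 days. Counting a Day 0 would add one day to each age (18 to 29 days now, 2 days with the added test) and leave the reduction unchanged. Section 5.1 allows the first-dose visit to be rescheduled, so 28 days is the scheduled maximum and not a cap.

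**Does the 12-day re-check close the gap?**

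On schedule, a patient is 17 − 12 = 5 to 28 − 12 = 16 days past the trigger at enrolment. Every on-schedule patient therefore qualifies for a re-check, but the provision is permissive, so no one has to be tested.

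**How many women?**

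The documents do not say. The assumed range is 0 to about 2 × 12 = 24, of whom at most 2 × 10 = 20 would receive tirzepatide. The upper end is only the enrolment ceiling, because men and women not of childbearing potential are also eligible.

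**The case against.** The strongest reply is that the plan already gives the site what it needs. The section 6 re-check covers clinical measurements that confirm eligibility, and pregnancy status is an eligibility matter, so a retest falls within its wording. Footnote h separately allows urine tests. Sexually active women must agree to two contraceptive methods. What remains is the difference between may and must. All of this stands as mitigation, but none of it ensures a test before Day 1. The protocol also allows more than one site (Appendix 6), so practice could differ between sites.

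A reader might infer that the plan contradicts itself by repeating safety tests on Day -1 while omitting pregnancy. The documents do not support that. SAP sections 9.6.4 and 9.6.5 use Day -1 as the baseline for chemistry, hematology and pancreatic enzymes, so those tests have an analysis purpose. Serology and the urine drug and alcohol screen, which serve eligibility, are also scheduled at screening only. Screening-only pregnancy testing follows the protocol's own pattern, and nothing in the documents sets a maximum age for the result.

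It is also fair to say that the only size available is the age of a result, not the probability of a missed pregnancy, and that weekly dosing continues to Day 106 or Day 162 with no scheduled test. Both limits stand. The first keeps the point modest. The second is outside its scope.

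**Conclusion.** The point holds as a low-cost safety improvement. For women of childbearing potential the last required pregnancy result is 17 to 28 days old at the scheduled first dose, and a Day -1 test would make it 1 day old.

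This rests on the schedule having no Day 0 and on the first dose being given on time. It does not depend on how many women of childbearing potential enrol, which may be none.

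Three stronger readings should be avoided. The plan does not prevent a site from testing before Day 1. No endpoint or analysis is affected. And a Day -1 urine test would reduce the chance of dosing in an undetected pregnancy without removing it, because it cannot exclude a very recent conception.

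**What to change.** 1. **Schedules.** Add a urine pregnancy test on Day -1 (Visit 3) for women of childbearing potential to both treatment-period tables, using the urine collected for urinalysis.
2. **Footnote h.** After the screening blood test, insert: *urine test on Day -1 for women of childbearing potential, with any positive urine result confirmed by a serum test before randomization*. Keep the existing allowance for urine tests at other times.
3. **Criterion [1b].** Add: *AND have a negative pregnancy test on Day -1, before randomization (urine; if the urine test is positive, a negative confirmatory serum test is required and determines eligibility)*. The clause needs its own time point because section 6.1 applies its criteria at screening. Serum must decide because section 6 allows no waivers and section 7.2 randomizes only patients who meet every criterion. A urine-only rule would bar a woman with a false positive.
4. **Appendix 2.** Give the pregnancy test its own matching footnote, leaving footnote c for FSH and microscopy. This also removes the reading that the screening serum test is discretionary.
5. **Section 5.1.** Add the pregnancy test to the results on which the first dose may be deferred, so that the visit can be rescheduled while a serum result is awaited. If pregnancy is confirmed, the patient is not randomized or dosed.

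**Cost.** Six short text edits: two schedule rows, footnote h, [1b], one Appendix 2 footnote and one phrase in section 5.1. Serum confirmation sits within footnote h and [1b]. There is one urine test per woman of childbearing potential admitted on Day -1, with no extra planned visit. Blood is drawn only after a positive urine result, and a false positive may occasionally cause a short delay.
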